6.4.4. Laboratory parameters

Not applicable.

6.4.5. Vital signs/Physical examination

Vital signs (i.e., systolic blood pressure, diastolic blood pressure and pulse rate) will be summarized at each timepoint as well as absolute changes from baseline.

6.4.6. Other safety parameters

Pregnancy

Considering female patients, at screening a serum pregnancy test should be performed for all women of childbearing potential. The proportion of patients who perform the pregnancy test together with the corresponding results will be provided. For female patients who do not perform pregnancy test the reason will be summarized (i.e., premenarchal, menopause, sterile, other).

| | |
|--|----------------------------------|
| | Statistical Analysis Plan |
| | Sponsor: Novartis |
| | Protocol: CRTH258AIT04 |

Ophthalmic examination:

A complete ophthalmic examination will be performed on the study eye at Screening, Baseline and Week 48 and may be performed at each in-between scheduled visit by the Investigator. At each visit the Investigators have to exclude the presence of any active intraocular inflammation in the study eye. This exam is also to be performed on the fellow eye at Screening and Week 48. Only data related to study eye will be summarized.

The ophthalmic exam may consist of the following:

- Biomicroscopy (slit lamp examination): the proportion of patients with any abnormal signs in anterior chamber (cells/flare) or Vitreous (cells/haze), the proportion of patients with any signs of Intraocular Inflammation (IOI) will be summarized at each visit. Moreover, the severity of anterior chamber cells and flare and the severity of vitreous cells and haze will be summarized considering the following categories:
 - for *Anterior Chamber cells*: 0 (<1), 0.5+ (1-5), 1+ (6-15), 2+ (16-25), 3+ (26-50), 4+ (>50).
 - for *Anterior Chamber flare*: 0 (None), 1+ (Faint), 2+ (Moderate: iris and lens details clear), 3+ (Marked: iris and lens details hazy), 4+ (Intense: fibrin or plastic aqueous).
 - for *Vitreous cells*: 0 (Clear: None), 0.5+ (Few opacities: 1-10 cells), 1+ (Scattered opacities: 11-20 cells), 2+ (Moderate opacities: 21-30 cells), 3+ (Many opacities: 31-100 cells).
 - for *Vitreous haze*: 0 (No haze), 0.5+ (Sometime subtle), 1+ (Permits a better definition of both optic nerve head and the retinal vessels), 2+ (Permits better visualization of the retinal vessels), 3+ (Optic nerve head is visible, but the borders are quite blurry), 4+ (Optic nerve head is obscured).
- Fundus (posterior segment) analyzed by the Color Fundus Photography (CFP). The Investigator's monitoring the disease activity of patients and in case of clinically significant abnormalities they will be collected and analyzed as adverse events. A description of qualitative parameters measured in the study eye at screening is provided as described in section 5.2 of the present document.
- Intraocular pressure (IOP) measurement will be summarized at each timepoint as well as absolute changes from baseline considering both pre-dose and post-dose assessments of IOP.

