- fundus (posterior segment) exam, which includes the evaluation of the vitreous, retina, macula, choroid, and optic nerve will be conducted at every scheduled and unscheduled visit by Investigator according to the clinical practice (fellow eye will be examined at the discretion of the investigator). Pupil dilation is to be performed at the discretion of the Investigator. An examination of the peripheral retina must also be performed, to ensure that the intravitreal injection can safely be performed as needed. Posterior segment examination must be performed carefully before each study treatment. The results of the examination including any abnormalities (e.g. vitreous cells/haze, retinal tear/detachment, hemorrhage and vascular occlusion, vasculitis, etc.) should be recorded in the source documents if appropriate. If there are any signs of IOI, vitreous cells and haze should be assessed using National Institutes of Health (NIH) grading system (Nussenblatt et al., 1985). The outcome of the examination will be documented in the source document (e.g., ophthalmic examination tool) and appropriate eCRF page as applicable. Any clinically significant abnormalities of either eye identified prior to signing the informed consent will be recorded on the medical history eCRF page, and on the adverse event page of the eCRF for any findings identified after signing the informed consent.
- intraocular pressure (IOP) measurement. Further details are reported in [Section 8.4.3](#).

Results of these procedures will be recorded as appropriate in the source documents. Clinically significant abnormalities (as judged by the Investigator) should be recorded as an AE in the eCRF.

Instruct the patient to contact the site for any changes in vision or any symptoms of inflammation between scheduled visits. Every effort should be made to bring the subject for immediate examination. In case of unscheduled visits these additional assessments will be documented in the source and appropriate eCRF pages. These images are requested to be uploaded onto the CRC portal.

When IOI, retinal vasculitis, and/or retinal artery occlusion (RAO) is present or suspected during a visit (both scheduled and unscheduled), investigators must perform thorough ophthalmic examination, [REDACTED]

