12.5.2 Safety endpoints

The safety set will be used for all safety analyses.

Safety summaries include only data from the on-treatment period. In particular, summary tables for adverse events (AEs) will summarize only on-treatment events, with a start date during the on-treatment period (treatment-emergent AEs).

The on-treatment period lasts from the date of first administration of study treatment to 30 days after the date of the last actual administration of the study treatment or the end of study, whichever is the latest.

Adverse events

All information obtained on adverse events will be summarized overall and listed by participant.

The number (and percentage) of participants with treatment-emergent adverse events (events started after the first dose of study medication) will be summarized in the following ways:

- by primary system organ class and preferred term.
- by primary system organ class, preferred term and maximum severity.

Separate summaries will be provided for study medication related treatment-emergent adverse events, death, serious treatment-emergent adverse events and other significant treatment-emergent adverse events leading to permanent treatment discontinuation.

A participant with multiple adverse events within a primary system organ class is only counted once towards the total of the primary system organ class.

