6.4.3. Adverse Events

Treatment-emergent adverse events (TEAEs) are defined as Adverse Events (AEs) that occurs on-treatment period, i.e., with a start date after or on the same date of first administration of study treatment.

General rules for AE Reporting

TEAEs will be descriptively summarized, whether non-TEAEs will only be listed.

TEAE summaries will be presented by primary SOC and PT sorted in alphabetical order within each SOC using the MedDRA dictionary.

If a patient report more than one TEAE coded to the same PT, in the analysis the patient will be counted only once in the incidence calculation for that PT. Similarly, if a patient has more than one TEAE in the same SOC, the patient will be counted only once in the total number of patients with an TEAE for that SOC.

The following TEAE summaries will be produced:

- General summary of TEAEs including the total number of events and absolute and relative frequency of patients with respectively at least one event of the following categories: TEAEs, treatment-emergent serious adverse events (TESAEs), ocular TEAEs, non-ocular TEAEs, suspected drug-related TEAEs, TEAEs with relationship to ocular injection procedure, TEAEs leading to interruption of treatment (defined as events with Action taken with drug of interest equal to “Drug interrupted”), TEAEs leading to withdrawn of treatment (defined as events with Action taken with drug of interest equal to “Drug withdrawn”), TEAEs leading to study discontinuation, fatal TESAEs.
- Summary of all TEAEs by SOC and PT;
- Summary of all TESAEs by SOC, PT and maximum severity.

| | |
|--|----------------------------------|
| | Statistical Analysis Plan |
| | Sponsor: Novartis |
| | Protocol: CRTH258AIT04 |

- Summary of all suspected drug-related TEAEs by SOC and PT;
- Summary of all suspected drug-related TEAEs by SOC, PT and maximum severity.
- Summary of all TEAEs with relationship to ocular injection procedure by SOC and PT;
- Summary of all TEAEs leading to interruption of treatment by SOC and PT;
- Summary of all TEAEs leading to withdrawn of treatment by SOC and PT;
- Summary of all TEAEs leading to study discontinuation by SOC and PT;
- Summary of all fatal TEAEs by SOC and PT;
- Summary of all TESAEs by SOC and PT;
- Summary of all TESAES by SOC, PT and maximum severity.

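### SAP 6.4.3 omits the protocol's table of all TEAEs by maximum severity and lists the serious-event version twice; separately, the vitreous-cell categories in SAP 6.4.6 have no place for counts above 100

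*SAP*

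**What the plan says.** **Adverse event tables.** Protocol 12.5.2 opens its list of adverse event tables with: "The number (and percentage) of participants with treatment-emergent adverse events (events started after the first dose of study medication) will be summarized in the following". Two breakdowns are then given: by SOC and PT, and "by primary system organ class, preferred term and maximum severity". Both apply to all TEAEs. Separate summaries for related, fatal, serious and discontinuation events come in addition.

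SAP 6.4.3 lists a table of all TEAEs by SOC and PT. Its next item is "Summary of all TESAEs by SOC, PT and maximum severity", where TESAEs are serious TEAEs. The last item in the list is the same serious-event severity table. The only other severity table is for suspected drug-related TEAEs.

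**Inflammation grades.** Protocol 8.4.2 states that, if there are signs of intraocular inflammation, "vitreous cells and haze should be assessed using National Institutes of Health (NIH) grading system". It does not reproduce the grades. SAP 6.4.6 gives categories for four scales. Anterior chamber cells are "0 (<1), 0.5+ (1-5), 1+ (6-15), 2+ (16-25), 3+ (26-50), 4+ (>50"). Flare ends at "4+ (Intense: fibrin or plastic aqueous") and vitreous haze at "4+ (Optic nerve head is obscured"). Vitreous cells end at "2+ (Moderate opacities: 21-30 cells), 3+ (Many opacities: 31-100 cells").

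**The concern.** Both passages specify outputs, and a programmer would follow them literally.

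On the first, a safety table that the protocol requires would not be produced. SAP 1.1 records much smaller departures, such as dropping the treatment-based prevalence of anxiety and depression, but is silent here. The reader of the study report would lose the severity profile of all adverse events taken together. Severity would also not be tabulated for events that the investigator judged neither serious nor suspected to be drug-related.

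On the second, a set of categories used to tabulate counts should cover every count that can occur. The vitreous-cell set does not. Intraocular inflammation is a main safety concern of this trial: Amendment 1 implemented urgent safety measures on retinal vasculitis and retinal vascular occlusion, which typically occur with such inflammation. The summary of its grades should therefore be complete.

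**Working it through.** No sample size, power or event figure bears on this point. The check sets the texts side by side.

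**1. Tables by SOC and PT in SAP 6.4.3, in SAP order**

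| Item | Events | Maximum severity shown? |
|---|---|---|
| 1 | All TEAEs | No |
| 2 | Serious TEAEs | Yes |
| 3 | Suspected drug-related TEAEs | No |
| 4 | Suspected drug-related TEAEs | Yes |
| 5 | Related to injection procedure | No |
| 6 | Treatment interrupted | No |
| 7 | Treatment withdrawn | No |
| 8 | Study discontinued | No |
| 9 | Fatal | No |
| 10 | Serious TEAEs | No |
| 11 | Serious TEAEs | Yes |

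Items 2 and 11 are the same table, so 11 listed − 1 repeated = 10 distinct. All TEAEs by maximum severity, the second table in protocol 12.5.2, is not among the 10.

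Items 3 and 4 form a pair (without, then with severity), and so do items 10 and 11. Item 1 is followed by item 2, which breaks the pattern. The simplest explanation is that item 2 was meant to read TEAEs. That is an inference from its position; the SAP does not say so.

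**2. Which events lose a severity table**

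- Serious TEAEs: covered by items 2 and 11.
- Suspected drug-related TEAEs: covered by item 4.
- Neither serious nor suspected drug-related: no severity table. A non-serious event attributed only to the injection procedure appears in items 1 and 5, both without severity.

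The additional ocular TEAE summaries in SAP 6.4.3 are by SOC, PT and eye, and do not mention severity either.

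**3. Whether listings fill the gap**

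Protocol 12.5.2 promises that all adverse event information will be listed by participant. SAP 6.4.3 names listings for deaths and for fatal, non-fatal serious, drug-related, procedure-related, interruption, withdrawal and study-discontinuation events, and for events that were not treatment-emergent. It names no listing of all TEAEs. A non-serious, unrelated TEAE that led to none of those actions therefore has no output named in the SAP that would show its severity. Procedure-related events do get a listing.

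**4. Coverage of the two cell-count scales in SAP 6.4.6**

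| Scale | Count ranges | Categories | Counts with no category |
|---|---|---|---|
| Anterior chamber cells | below 1; 1–5; 6–15; 16–25; 26–50; above 50 | 6 | None |
| Vitreous cells | none; 1–10; 11–20; 21–30; 31–100 | 5 | 101 and above |

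Three of the four scales have a 4+ category. Only vitreous cells stop at 3+, and that category has an upper bound.

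**The case against.** **The table looks like a slip and loses no data.** This is largely fair. Protocol 10.1.1 has every adverse event graded mild, moderate or severe, so the data exist. The position of the duplicate suggests a one-word error. A reader might infer that the SAP chose to cut back severity reporting; nothing in the documents supports that. The SAP as written still does not produce a table that the protocol requires.

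**The omission barely touches the key risk.** This also stands in part. Inflammation, vasculitis or occlusion judged serious or drug-related keeps a severity table. What is lost is the overall picture and the remaining events.

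**The most severe inflammation would have no grade.** A reader might infer this from the two gaps together, but it goes too far. Anterior chamber cells, flare and vitreous haze all reach 4+. An eye with more than 100 vitreous cells can still receive a haze grade and count among eyes with signs of inflammation. The missing adverse event table removes no inflammation grade.

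**The vitreous categories depart from the protocol's scale.** This cannot be claimed. Protocol 8.4.2 names a grading system without giving its grades, so there is no protocol scale from which to show an undeclared change. The point rests only on the SAP's own bounded top category.

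**An eye above 100 cells would vanish.** Not necessarily. SAP 4.1 bases percentages on totals with a missing category shown, so such an eye might appear there. It would still not be shown by grade.

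**The number affected could be estimated from protocol 4.5.** The protocol quotes inflammation-related events in 5.3% of females and 3.2% of males in the pivotal trials. Applied to all 122 enrolled patients, that gives 122 × 0.032 = 3.9 to 122 × 0.053 = 6.5. These are rates of any such event, by sex and from other trials. They do not measure vitreous-cell counts above 100 and should not be used to size this gap.

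**Conclusion.** Both points hold as stated, and they are separate.

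The main one is the missing table of all TEAEs by maximum severity. It is absent from the SAP, an existing table is listed twice instead, and the difference from protocol 12.5.2 is not declared in SAP 1.1. Its size is one of the two tables that the protocol sets for all TEAEs. The consequence is confined to the all-event severity overview and to events that are neither serious nor suspected drug-related. This rests on reading the SAP list as the complete set of planned adverse event tables.

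The smaller one is that vitreous-cell counts above 100 have no category. The number of eyes affected is unknown and may be zero, because the documents give no rate for such counts and do not show the eCRF options.

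Neither point affects the primary analysis or the management of patients.

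**What to change.** 1. In SAP 6.4.3, change TESAEs to TEAEs in the first of the two identical severity items, directly after the table of all TEAEs by SOC and PT. Keep the later serious-event table. This removes the duplicate and restores the protocol 12.5.2 table.
2. In SAP 6.4.6, add a vitreous-cell category for more than 100 cells, labelled consistently with the grading system named in protocol 8.4.2, and map any such recorded entries to it. If the eCRF options also stop at 3+, state how higher counts were entered and check the source records of the few eyes with inflammation.

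The cost is two lines of SAP wording and one standard table from data already collected, plus the source check if it proves necessary.

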Visit number	1	2	3	4	5	6	7-13	14
Weeks	Up to 2 weeks	1	4	8	12	16	20 to 44 ¹	48
Obtain informed consent	X							
Demography	X							
Inclusion/exclusion criteria	X	X						
Relevant medical history/current medical history	X							
Vital Signs ^{2, 3}	X	X	X	X	X	X	X	X
Prior/Concomitant systemic medications	X	X	X	X	X	X	X	X
Prior/Concomitant ocular medications	X	X	X	X	X	X	X	X
Serum β-hCG Pregnancy Test ⁴	X							
Urine Pregnancy Test ⁴		X	X	X	X	X	X	X
BCVA score (ETDRS)	X	X	X	X	X	X	X	X
IOP measurement ⁵	X	X	X	X	X	X	X	X
Complete ophthalmic examination ^{2, 6}	X	X	X	X	X	X	X	X
SD-OCT ⁹	X	X	X	X	X	X	X	X
OCTA	X	X	X	X	X	X	X	X
FA ⁹	X							X
ICGA	X							X
Color Fundus Photography (CFP)	X	X	X	X	X	X	X	X
EQ-5D-5L		X						X
HADS		X						X

Period	Screening	Treatment						End of Study
Visit Name	Screening*	Baseline Day 1	W4	W8	W12	W16	Treatment visits	W48*
Visit number	1	2	3	4	5	6	7-13	14
Weeks	Up to 2 weeks	1	4	8	12	16	20 to 44 ¹	48
Disease Activity Assessment ⁷						X	X	X
Study drug administration		X	X	X		X ⁸	X ⁸	X ⁸
Adverse Events	X	X	X	X	X	X	X	X

X = assessment to be recorded in the clinical database or received electronically from a vendor

* At Screening and Week 48 the fellow eye will be assessed for BCVA, ophthalmic examination, IOP, SD-OCT, OCTA, CFP, FA and ICGA. For the other visits it will be assessed according to clinical practice

¹ Treatment visits will take place every 8 or 12 weeks starting from Visit 4 (Week 8), according to Investigator's decision at each assessment visit

² Vital signs collection and/or complete ophthalmic examination are to be performed at each visit. The Investigator have to exclude the presence of any active intraocular inflammation in the study eye.

³ Vital signs include sitting blood pressure and pulse rate.

⁴ Women of childbearing potential only. A positive urine test should be confirmed by a Serum β-hCG Pregnancy test.

⁵ IOP measurement is to be performed prior and 30-60 minutes after each treatment IVT injection

⁶ Complete ophthalmic examination include slit lamp exam, IOP measurement and fundus exam, for safety assessment before and after IVT. Pupil dilation optional according to local practice.

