8.4.3 IOP measurement

A measurement of IOP in the study eye will be conducted at each post-Screening visit when the treatment administration is foreseen (pre-dose and post-dose). In the fellow eye, IOP will be assessed at Screening and Week 48. The same method of tonometry should be used throughout the study for each participant. Treatment and close monitoring of IOP should be performed by the Investigator for any non-transient elevation in intraocular pressure (≥ 25 mmHg). Intravitreal injection is not recommended unless normalization of the IOP has been achieved. Post-dose IOP should be assessed approximately within 60 minutes after injection and if ≥ 25 mmHg, assessment should be repeated until back to normal. Monitoring of optic nerve head perfusion after injection may be appropriate, at the discretion of the Investigator and/or according to local requirements/practices. Results of these procedures will be recorded as appropriate in the source documents. Clinically significant abnormalities (as judged by the Investigator) should be recorded as an AE in the eCRF.

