4. DEFINITIONS AND GENERAL METHODOLOGY

4.1. General Methodology

Statistical tables, listings and analyses will be produced using SAS® release 9.4 (64 bit) or later (SAS Institute, Inc., Cary, NC, USA).

The data from all sites will be pooled and summarized.

Continuous data will be summarized with mean, standard deviation (SD), median, Q1, Q3, minimum and maximum. Categorical data will be presented by absolute and relative frequencies (n and %) or contingency tables. The percentage calculation will be based on total values (i.e., count will be shown also in the missing category, unless otherwise specified).

Unless stated otherwise, a two-sided alpha level 0.05 will be considered. No alpha level adjustment will be carried out for primary and secondary outcome variables, unless otherwise specified.

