Participants who sign an informed consent form and subsequently found to be ineligible will be considered a screen failure. The reason for screen failure should be recorded on the appropriate eCRF page. The demographic information, informed consent, and Inclusion/Exclusion eCRF pages must also be completed for screen failure participants. No other data will be entered into the clinical database for participants who are screen failures, unless the participant experienced a serious adverse event (SAE) during the screening phase.

Definition of Baseline

Baseline date (day 1) is defined as the date of the first treatment administration, i.e. the date of Visit 2.

First/Last Administration of Study Treatment

The date of first brolucizumab administration is the first date of injection reported in the BROLUCIZUMAB DOSAGE ADMINISTRATION RECORD eCRF page.

The date of last brolucizumab intake is the last treatment date reported in the TREATMENT DISPOSITION eCRF page.

Study day

| | |
|--|---|
| | Statistical Analysis Plan |
| | Sponsor: Novartis Protocol: CRTH258AIT04 |

Study day is defined as the number of days from the first treatment administration date (i.e., reference date) to the visit/event date. If the visit/event date is on the same day of after the reference date, it is calculated as:

Study day = Visit/event date - first brolucizumab administration date + 1 day.

If the visit/event date is before the first brolucizumab injection date, then the study day is calculated as follows:

Study day = Visit/event date - first brolucizumab administration date.

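### The SAP plans no same-visit post-minus-pre IOP change and no count at the protocol's own 25 mmHg level, and it leaves the Day 1 reference and the handling of repeat readings undefined

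*SAP*

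**What the plan says.** Protocol Table 8-1, note 5, sets the paired readings: "IOP measurement is to be performed prior and 30-60 minutes after each treatment IVT injection". Protocol 8.4.3 adds a level and a repeat rule: "Post-dose IOP should be assessed approximately within 60 minutes after injection and if ≥ 25 mmHg, assessment should be repeated until back to normal". The same section uses 25 mmHg again for non-transient elevations, and it sends notable findings to the adverse event pages: "Clinically significant abnormalities (as judged by the Investigator) should be recorded as an AE in the eCRF".

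The analysis is one sentence in SAP 6.4.6: "Intraocular pressure (IOP) measurement will be summarized at each timepoint as well as absolute changes from baseline considering both pre-dose and post-dose assessments of IOP". SAP 4.1 fixes the statistics: "Continuous data will be summarized with mean, standard deviation (SD), median, Q1, Q3, minimum and maximum". SAP 4.2 defines the reference day: "Baseline date (day 1) is defined as the date of the first treatment administration, i.e. the date of Visit 2". That is an injection day, so it carries both a pre-dose and a post-dose reading. The SAP does not name one of them as the IOP reference. It also gives no rule for choosing among repeated post-dose readings. Protocol 12.5.2, on safety endpoints, plans no IOP analysis.

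**The concern.** A reading before and a reading after the same injection form a natural pair, and their difference is the most direct estimate of the pressure rise at that injection. The SAP instead states its change relative to Day 1 for both readings. A post-dose change from the Day 1 pre-dose value mixes the acute rise with any drift since Day 1. A post-dose change from the Day 1 post-dose value removes any rise that is constant across injections.

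The protocol names a pressure level that prompts action, yet no table counts how often that level was reached. Repeat readings arise exactly when the first one is high, so the choice of reading decides whether a high value enters the table at all. At stake is a clear description of a procedural safety finding: how large and how variable the rise is, and how many patients had a reading at the protocol's own level.

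**Working it through.** The documents give no IOP mean, SD or rate, so there is no planned figure to reproduce. Every IOP value below is an assumption for illustration. The inputs from the documents are 122 enrolled patients (SAP 3.1), the 25 mmHg level (Protocol 8.4.3), the summary statistics (SAP 4.1) and the injection schedule (Protocol Table 8-1, note 1). On stable q12w, injections fall at Weeks 0, 4, 8, 20, 32 and 44, which is 6. On stable q8w they fall at Weeks 0, 4, 8, 16, 24, 32, 40 and 48, which is 8 if the Week 48 injection is given and 7 if not.

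**1. The mean rise is recoverable under conditions.** If both changes use the same Day 1 reading and the same patients contribute, then

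mean(post − base) − mean(pre − base) = mean(post − pre).

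In one simulated set of 122 patients both sides gave 4.10 mmHg. With about 10% of post-dose readings removed, the paired mean was 4.11 and the difference of the two reported means was 4.19. If post-dose is referred to Day 1 post-dose, a constant rise of, say, 4 mmHg gives 4 − 4 = 0 in the change column. The observed pre- and post-dose columns would still show it.

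**2. The spread is not recoverable after Day 1.** The SD of the paired rise is √(s₁² + s₂² − 2·r·s₁·s₂), where r is the same-visit correlation of pre- and post-dose IOP. The planned tables give s₁ and s₂. The SDs of the change columns carry information on each reading's correlation with Day 1, not on r. With assumed s₁ = 3 and s₂ = 5:

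| r | SD of rise (mmHg) |
|---|---|
| 0 | 5.83 |
| 0.3 | 5.00 |
| 0.5 | 4.36 |
| 0.7 | 3.61 |
| 0.9 | 2.65 |

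There is one exception. If the reference is the Day 1 pre-dose reading, the Day 1 post-dose change is itself the paired rise for the first injection.

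**3. The count at 25 mmHg is not recoverable.** Take post-dose IOP as normal with mean 16, 18 or 20 and SD 3, 5 or 7 mmHg, with 122 patients at a visit. The share at or above 25 is 1 − Φ((25 − mean)/SD), and the chance that the visit maximum reaches 25 is 1 − (1 − share)¹²².

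| Mean, SD | Share ≥ 25 | Expected of 122 | Q3 | P(maximum ≥ 25) |
|---|---|---|---|---|
| 16, 3 | 0.13% | 0.2 | 18.0 | 0.15 |
| 18, 3 | 0.98% | 1.2 | 20.0 | 0.70 |
| 16, 5 | 3.6% | 4.4 | 19.4 | 0.988 |
| 18, 5 | 8.1% | 9.9 | 21.4 | about 1 |
| 20, 7 | 23.8% | 29.0 | 24.7 | about 1 |

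In all nine combinations Q3 is below 25. A maximum below 25 fixes the count at zero. A maximum at or above 25 is compatible with anything from 1 patient to about 29 here.

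**4. Patients affected at any time cannot be built from visit tables.** Suppose 5% of injections reach the level and each patient has 6. If it is always the same patients, 5% are ever affected. If injections are independent, it is 1 − 0.95⁶ = 26.5%. If a different patient is affected each time, it is 6 × 5% = 30%. At 1% per injection the three figures are 1%, 5.9% and 6%. Visit summaries do not distinguish these cases.

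**The case against.** A reader might infer that IOP is reported only as mean change from baseline, so that the injection rise is never estimated and high pressures disappear into averages. The documents do not support that. SAP 6.4.6 plans observed values as well as changes, for both readings, and SAP 4.1 adds the median, quartiles, minimum and maximum. The mean rise follows approximately from the planned columns, and in most of the scenarios above the visit maximum would reveal that a high value occurred. Clinically significant elevations become adverse events, SAP 6.4.3 tabulates events related to the injection procedure, and Protocol Section 12 promises data listings. All of this stands.

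A reader might also infer that the last, normalised repeat would be analysed and the peak erased. Protocol 8.4.3 requires that "assessment should be repeated until back to normal", but nothing says that the last value is the one used. The gap is a missing rule, not a wrong one.

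It is also fair to say that the documents tie the paired readings to clinical monitoring, not to estimating an injection effect, and that the SAP already goes beyond Protocol 12.5.2. That limits the point's weight. It does not supply the missing quantities. Adverse event capture rests on Investigator judgment, so it is not a count at a fixed level, and a listing leaves the tabulation to its reader. The SAP uses categories elsewhere: graded inflammation signs in the same section, and gains and losses of 5, 10 and 15 letters for visual acuity in 6.3.2.3.

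The two post-dose timings (30 to 60 minutes in Table 8-1, approximately within 60 minutes in 8.4.3) overlap, and nothing here depends on the difference.

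**Conclusion.** The point holds as a minor gap in a descriptive safety table. The planned tables would give an approximate mean rise and an indication that high values exist. They would not give the spread of the rise at injections after Day 1. Unless every relevant maximum is below 25 mmHg, they would also not give the number of injections or patients at or above that level. Two definitions are open: the Day 1 reference reading, and the post-dose reading to use when there are several.

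The size of the loss cannot be stated in trial units because the documents contain no IOP data. The SD range of 2.65 to 5.83 mmHg and the 0.1% to 23.8% range rest on assumed SDs, correlations and normality. The any-time figures rest on assumed rates of 1% and 5% per injection. The absence of the paired change and of the count does not depend on these assumptions. The primary analysis and the sample size are unaffected.

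**What to change.** In SAP 6.4.6:

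- Replace the post-dose change from baseline with same-visit post-dose minus pre-dose IOP at each injection visit, with the SAP 4.1 statistics, in patients who have both readings.
- Add n (%) of injections, and n (%) of patients at any time, with post-dose IOP ≥ 25 mmHg.
- State the post-dose reading used: the highest of the visit, or the first if repeats are held only in source documents. Protocol 8.4.3 says results go to source as appropriate and the eCRF is not shown, so check this first.
- Keep the pre-dose change for drift, and name the Day 1 pre-dose reading as its reference.

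The cost is one redefined column, two added rows and two sentences of definition. The basic pairs are already in the planned summary, so no new measurement is needed. With 122 patients the added proportion would be usefully precise. The exact 95% intervals are 0 to 3.0% for 0/122, 0.5 to 7.0% for 3/122 (2.5%), 1.8 to 10.4% for 6/122 (4.9%) and 5.2 to 16.6% for 12/122 (9.8%).
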